### APPENDIX B: RECIST v1.1

# RESPONSE EVALUATION CRITERIA IN SOLID TUMOURS, VERSION 1.1 (RECIST V1.1)

Selected sections from the Response Evaluation Criteria in Solid Tumours, Version 1.1 (RECIST v1.1), (Eisenhauer et al. 2009) are presented below, with slight modifications from the original publication and the addition of explanatory text as needed for clarity.

### 1 TUMOUR MEASURABILITY

At screening, tumour lesions/lymph nodes will be categorised as measurable or non-measurable as described below. All measurable and non-measurable lesions should be assessed at Screening and at subsequent protocol-specified tumour assessment timepoints. Additional assessments may be performed as clinically indicated for suspicion of progression.

### 1.1 Measurable Lesions

### 1.1.1 Tumour Lesions

Tumour lesions must be accurately measured in at least one dimension (longest dimension in the plane of measurement is to be recorded) with a minimum size as follows:

- 10 mm by computed tomography (CT) or magnetic resonance imaging (MRI) scan (CT/MRI scan slice thickness/interval ≤ 5 mm)
- 10-mm calliper measurement by clinical examination (lesions that cannot be accurately measured with callipers should be recorded as non-measurable)
- 20 mm by chest X-ray

# 1.1.2 Malignant Lymph Nodes

To be considered pathologically enlarged and measurable, a lymph node must be  $\geq 15$  mm in the short axis when assessed by CT scan (CT scan slice thickness recommended to be  $\leq 5$  mm). At Baseline and follow-up, only the short axis will be measured and followed. Additional information on lymph node measurement is provided below (see "Identification of Target and Non-Target Lesions" and "Calculation of Sum of Dimensions").

### 1.2 Definition of Non-Measurable Lesions

Non-measurable tumour lesions encompass small lesions (longest dimension < 10 mm or pathological lymph nodes with short axis ≥ 10 mm but < 15 mm) as well as truly non-measurable lesions. Lesions considered truly non-measurable include leptomeningeal disease, ascites, pleural or pericardial effusion, inflammatory breast disease, lymphangitic involvement of skin or lung, peritoneal spread, and abdominal mass/abdominal organomegaly identified by PE that is not measurable by reproducible imaging techniques.

agalin A subsidiary of BIO	PRIVILEGED & CONFIDENTIAL	
Investigational Product: AGI-134	A Phase I/IIa, multicentre, two-parts, open label study designed to evaluate the safety and tolerability of escalating	Protocol No. AGI-134.FIM.101
Phase: I/IIa		Version 6.1 31 May 2021

# 1.3 Special Considerations Regarding Lesion Measurability

Bone lesions, cystic lesions, and lesions previously treated with local therapy require particular comment, as outlined below.

#### 1.3.1 Bone Lesions

- Bone scans, PET tomography scans, and plain films are not considered adequate imaging techniques for measuring bone lesions. However, these techniques can be used to confirm the presence or disappearance of bone lesions.
- Lytic bone lesions or mixed lytic-blastic lesions with identifiable soft tissue components
  that can be evaluated by cross-sectional imaging techniques such as CT or MRI can be
  considered measurable lesions if the soft tissue component meets the definition of
  measurability described above.
- Blastic bone lesions are non-measurable.

# 1.3.2 Cystic Lesions

- Lesions that meet the criteria for radiographically defined simple cysts should not be considered malignant lesions (neither measurable nor non-measurable) because they are, by definition, simple cysts.
- Cystic lesions thought to represent cystic metastases can be considered measurable lesions
  if they meet the definition of measurability described above. However, if non-cystic lesions
  are present in the same subject, these are preferred for selection as target lesions.

### 1.3.3 Lesions with Prior Local Treatment

 Tumour lesions situated in a previously irradiated area or in an area subjected to other locoregional therapy are usually not considered measurable unless there has been demonstrated progression in the lesion.

### 2 METHODS FOR ASSESSING LESIONS

All measurements should be recorded in metric notation, using calipers if clinically assessed. All Baseline evaluations should be performed as close as possible to the treatment start and never more than 4 weeks before the beginning of the treatment.

The same method of assessment and the same technique should be used to characterise each identified and reported lesion at Baseline and during the study. Imaging-based evaluation should always be the preferred option.

### 2.1 Clinical Lesions

Clinical lesions will only be considered measurable when they are superficial and  $\geq 10$  mm in dimension as assessed using calipers (e.g., skin nodules). For the case of skin lesions, documentation by colour photography, including a ruler to estimate the size of the lesion, is suggested.

Protocol AGI-134.FIM.101 CONFIDENTIAL Page 102 of 108

agalin A subsidiary of BIO	PRIVILEGED & CONFIDENTIAL	
Investigational Product: AGI-134	A Phase I/IIa, multicentre, two-parts, open label study designed to evaluate the safety and tolerability of escalating	Protocol No. AGI-134.FIM.101
Phase: I/IIa		Version 6.1 31 May 2021

# 2.2 Chest X-Ray

Chest CT is preferred over chest X-ray, particularly when progression is an important endpoint, because CT is more sensitive than X-ray, particularly in identifying new lesions. However, lesions on chest X-ray may be considered measurable if they are clearly defined and surrounded by aerated lung.

### 2.3 CT and MRI Scans

CT is the best currently available and reproducible method to measure lesions selected for response assessment. In this guideline, the definition of measurability of lesions on CT scan is based on the assumption that CT slice thickness is  $\leq 5$  mm. When CT scans have slice thickness of > 5 mm, the minimum size for a measurable lesion should be twice the slice thickness. MRI is also acceptable.

If prior to enrolment, it is known that a patient is unable to undergo CT scans with intravenous (IV) contrast because of allergy or renal insufficiency, the decision as to whether a non-contrast CT or MRI (without IV contrast) will be used to evaluate the patient at Baseline and during the study should be guided by the tumour type under investigation and the anatomic location of the disease. For patients who develop contraindications to contrast after baseline contrast CT is done, the decision as to whether non-contrast CT or MRI (enhanced or non-enhanced) will be performed should also be based on the tumour type and the anatomic location of the disease and should be optimised to allow for comparison with prior studies, if possible. Each case should be discussed with the radiologist to determine if substitution of these other approaches is possible and, if not, the patient should be considered not-evaluable from that point forward. Care must be taken in measurement of target lesions and interpretation of non-target disease or new lesions on a different modality, because the same lesion may appear to have a different size using a new modality.

# 2.4 Endoscopy, Laparoscopy, Ultrasound, Tumour Markers, Cytology, Histology

Endoscopy, laparoscopy, ultrasound, tumour markers, cytology, and histology cannot be utilised for objective tumour evaluation.

### 3 ASSESSMENT OF TUMOUR BURDEN

To assess objective response or future progression, it is necessary to estimate the overall tumour burden at Baseline and use this as a comparator for subsequent measurements.

# 3.1 Identification of Target and Non-Target Lesions

When more than one measurable lesion is present at Baseline, all lesions up to a maximum of five lesions total (and a maximum of two lesions per organ) representative of all involved organs should be identified as target lesions and will be recorded and measured at Baseline. This means that, for instances in which patients have only one or two organ sites involved, a maximum of two lesions (one site) and four lesions (two sites), respectively, will be recorded. Other lesions (albeit measurable) in those organs will be considered non-target lesions.

agalin A subsidiary of Bio	nnune DLINERX	PRIVILEGED & CONFIDENTIAL
Investigational Product: AGI-134		Protocol No. AGI-134.FIM.101
Phase: I/IIa	doses of AGI-134 in unresectable/metastatic solid tumours.	Version 6.1 31 May 2021

Target lesions should be selected on the basis of their size (lesions with the longest dimension) and be representative of all involved organs, but in addition should lend themselves to reproducible repeated measurements. It may be the case that, on occasion, the largest lesion does not lend itself to reproducible measurement, in which circumstance the next largest lesion that can be measured reproducibly should be selected.

Lymph nodes merit special mention because they are normal anatomical structures that may be visible by imaging even if not involved by tumour. As noted above, pathological nodes that are defined as measurable and may be identified as target lesions must meet the criterion of a short axis of  $\geq 15$  mm by CT scan. Only the short axis of these nodes will contribute to the Baseline sum. The short axis of the node is the dimension normally used by radiologists to judge if a node is involved by solid tumour. Lymph node size is normally reported as two dimensions in the plane in which the image is obtained (for CT, this is almost always the axial plane; for MRI, the plane of acquisition may be axial, sagittal, or coronal). The smaller of these measures is the short axis. For example, an abdominal node that is reported as being 20 mm  $\times$  30 mm has a short axis of 20 mm and qualifies as a malignant, measurable node. In this example, 20 mm should be recorded as the node measurement. All other pathological nodes (those with short axis  $\geq$  10 mm but < 15 mm) should be considered non-target lesions. Nodes that have a short axis of < 10 mm are considered non-pathological and should not be recorded or followed.

All lesions (or sites of disease) not selected as target lesions (measurable or non-measurable), including pathological lymph nodes, should be identified as non-target lesions and should also be recorded at Baseline. Measurements are not required. It is possible to record multiple non-target lesions involving the same organ as a single item on the Case Report Form (CRF) (e.g., "multiple enlarged pelvic lymph nodes" or "multiple liver metastases").

# 3.2 Calculation of Sum of Dimensions

A sum of the dimensions (longest dimension for non-lymph node lesions, short axis for lymph node lesions) will be calculated for all target lesions at baseline and at each subsequent tumour assessment as a measure of tumour burden.

# 3.2.1 Measuring Lymph Nodes

Lymph nodes identified as target lesions should always have the actual short axis measurement recorded (measured in the same anatomical plane as the baseline examination), even if the node regresses to < 10 mm during the study. Thus, when lymph nodes are included as target lesions, the sum of dimensions may not be zero even if CR criteria are met, because a normal lymph node is defined as having a short axis of < 10 mm.

### 3.2.2 Measuring Lesions That Become Too Small to Measure

During the study, all target lesions (lymph node and non-lymph node) recorded at baseline should have their actual measurements recorded at each subsequent evaluation, even when very small (e.g., 2 mm). However, sometimes lesions or lymph nodes that are recorded as target lesions at Baseline become so faint on CT scan that the radiologist may not feel comfortable assigning an exact measurement and may report them as being too small to measure. When this occurs, it is important that a value be recorded on the CRF, as follows:

agalin A subsidiary of BIO	PRIVILEGED & CONFIDENTIAL	
Investigational Product: AGI-134	A Phase I/IIa, multicentre, two-parts, open label study designed to evaluate the safety and tolerability of escalating	Protocol No. AGI-134.FIM.101
Phase: I/IIa	doses of AGI-134 in unresectable/metastatic solid tumours.	Version 6.1 31 May 2021

- If it is the opinion of the radiologist that the lesion has likely disappeared, the measurement should be recorded as 0 mm.
- If the lesion is believed to be present and is faintly seen but too small to measure, a default value of 5 mm should be assigned and "too small to measure" should be ticked. (Note: It is less likely that this rule will be used for lymph nodes because they usually have a definable size when normal and are frequently surrounded by fat such as in the retroperitoneum; however, if a lymph node is believed to be present and is faintly seen but too small to measure, a default value of 5 mm should be assigned in this circumstance as well, and "too small to measure" should also be ticked).

To reiterate, however, if the radiologist is able to provide an actual measurement, that should be recorded, even if it is < 5 mm, and in that case "too small to measure" should not be ticked.

# 3.2.3 Measuring Lesions That Split or Coalesce on Treatment

When non-lymph node lesions fragment, the longest dimensions of the fragmented portions should be added together to calculate the sum of dimensions. Similarly, as lesions coalesce, a plane between them may be maintained that would aid in obtaining maximal dimension measurements of each individual lesion. If the lesions have truly coalesced such that they are no longer separable, the vector of the longest dimension in this instance should be the maximum longest dimension for the coalesced lesion.

### 3.2.4 Evaluation of Non-Target Lesions

Measurements are not required for non-target lesions, except that malignant lymph node non-target lesions should be monitored for reduction to < 10 mm in short axis. Non-target lesions should be noted at Baseline and should be identified as "present (Non-CR/Non-PD)" or "absent (CR)" and (in rare cases) may be noted as "Unequivocal progression (PD)" at subsequent evaluations. In addition, if a lymph node lesion shrinks to a non-malignant size (short axis < 10 mm), this should be captured on the CRF as part of the assessment of non-target lesions.

### 4 RESPONSE CRITERIA

### 4.1 Criteria for Target Lesions

Definitions of the criteria used to determine objective tumour response for target lesions are provided below:

- Complete response (CR): Disappearance of all target lesions
   Any pathological lymph nodes must have reduction in short axis to < 10 mm.

- Partial response (PR): At least a 30% decrease in the sum of dimensions of all target lesions, taking as reference the Baseline sum of dimensions, in the absence of CR
- Progressive disease (PD): At least a 20% increase in the sum of dimensions of target lesions, taking as reference the smallest sum of dimensions on study (including Baseline)

Protocol AGI-134.FIM.101 CONFIDENTIAL Page 105 of 108

agalin A subsidiary of Bio	nnune DLINERX	PRIVILEGED & CONFIDENTIAL
Investigational Product: AGI-134		Protocol No. AGI-134.FIM.101
Phase: I/IIa	doses of AGI-134 in unresectable/metastatic solid tumours.	Version 6.1 31 May 2021

In addition to the relative increase of 20%, the sum of dimensions must also demonstrate an absolute increase of  $\geq 5$  mm.

 Stable disease (SD): Neither sufficient shrinkage to qualify for CR or PR nor sufficient increase to qualify for PD

# 4.2 Criteria for Non-Target Lesions

Definitions of the criteria used to determine the tumour response for the group of non-target lesions are provided below. While some non-target lesions may actually be measurable, they need not be measured and instead should be assessed only qualitatively at the timepoints specified in the schedule of activities.

 CR: Disappearance of all non-target lesions and (if applicable) normalisation of tumour marker level

All lymph nodes must be non-pathological in size (< 10 mm short axis).

- Non-CR/Non-PD: Persistence of one or more non-target lesions and/or (if applicable)
  maintenance of tumour marker level above the normal limits
- PD: Unequivocal progression of existing non-target lesions

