# Part 2- AGI-134 at the RP2D

Protocol AGI-134.FIM.101

This part is designed to assess the safety, tolerability and biological activity of AGI-134 at the RP2D in subjects with either deep or superficial unresectable/metastatic solid tumours. Subjects with selected unresectable/metastatic solid tumours, either superficial or deep lesions, will be enrolled and receive intratumoural injections of AGI-134 according to the injected tumour dimensions in one or more tumours according to the judgement of the PI and the instructions included in the *Administration of AGI-134 and Tumour Biopsy Procedures in Study AGI-134.FIM.101* document, up to, but not exceeding the RP2D at each dosing, every three weeks for up to 4 cycles.

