#### Part 1:

- Unresectable superficial/palpable tumour feasible for intratumoural injection from any solid tumour, and
- A metastatic/secondary lesion that can be assessed for abscopal effect and from which a biopsy can be taken.

At least one unresectable lesion feasible for intratumoural injection and biopsy, and

Protocol AGI-134.FIM.101 CONFIDENTIAL Page 36 of 108

<sup>7 Tumour lesions situated in a previously irradiated area are considered evaluable if progression has been demonstrated in such lesions.

agalin A subsidiary of BIO		PRIVILEGED & CONFIDENTIAL
Investigational Product: AGI-134	designed to evaluate the safety and tolerability of escalating doses of AGI-134 in unresectable/metastatic solid tumours.	Protocol No. AGI-134.FIM.101
Phase: I/IIa		Version 6.1 31 May 2021

- A metastatic/secondary lesion that can be assessed for abscopal effect and from which a biopsy can be taken. The lesions should be from one of the following selected metastatic tumours:
- The lesions should be from one of the following selected metastatic tumours:
  - Skin melanoma patients with progression on up to two lines immunotherapy, whether or not patient was previously treated with chemotherapy or targeted therapy.
  - Patients with superficial (either visible or palpable) lesions that can be injected and biopsied from the following indications:
    - a. Skin melanoma treated with three previous lines of immunotherapy, upon discussion and approval by the Sponsor.
    - b. Any squamous cell carcinoma (SCC)
    - c. Mucosal melanoma
    - d. Other Skin cancers, such as: Basocellular carcinoma, Merkel cell carcinoma
    - e. Any other superficial/palpable tumour, either primary or metastasis that are available for injection and biopsy upon discussion with and approval by the Sponsor.
- 5. Patients who received prior treatment with CPI should have remained on treatment with one of the immunotherapy treatments for at least 4 months or have stopped treatment earlier than that due to toxicity rather than disease progression.
- 6. Subjects who are willing to undergo tumour biopsies, according to protocol requirements.
- 7. Tumour size:

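### Appendix B chooses target lesions without regard to injection status, so the un-injected lesion required for abscopal assessment need not be measured in some subjects, and pooled sums cannot show where a response came from.

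*Combined protocol and SAP*

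**What the plan says.** Section 4.1, criterion 4, requires in both parts, besides a lesion to inject, "A metastatic/secondary lesion that can be assessed for abscopal effect and from which a biopsy can be taken". Criterion 8 asks only that this second lesion be evaluable and amenable to biopsy; it need not be measurable or a target.

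Section 5.12 has response assessed by RECIST v1.1 as set out in Appendix B. Appendix B 3.1 takes as targets "all lesions up to a maximum of five lesions total (and a maximum of two lesions per organ) representative of all involved organs". Where few organs are involved, "a maximum of two lesions (one site) and four lesions (two sites), respectively, will be recorded". Selection goes by size, with representativeness and reproducible measurement as further conditions. Whether a lesion is injected plays no part. Beyond the cap, "Other lesions (albeit measurable) in those organs will be considered non-target lesions", and for non-target lesions at Baseline "Measurements are not required". On study, Appendix B 4.2 adds: "While some non-target lesions may actually be measurable, they need not be measured and instead should be assessed only qualitatively". Appendix B 3.2.4 makes one exception: malignant non-target nodes are followed against a 10 mm short-axis threshold.

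More than one lesion may be injected. Part 1 allows the volume to be divided with at least 1 mL per tumour, and in Part 2 (Section 3) injection is "in one or more tumours according to the judgement of the PI".

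**The concern.** The proposed mechanism is systemic: injecting one lesion should provoke a response against others. The clinical observation closest to that claim is the change in size of lesions that were not injected. The measurement rules do not secure it. They can leave such a lesion with a qualitative entry only, and where it is measured they add it to the injected lesions in one sum. A RECIST response may then be entirely local, while real shrinkage at a distance may leave no numerical trace. A baseline diameter that was not recorded can be recovered only by re-reading the images, where they allow it.

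**Working it through.** **Target slots.** Inputs are the caps in Appendix B 3.1. Slots = min(5, 2 × number of organ sites), which gives 2, 4 and 5 for one, two and three sites. This reproduces the stated 2 and 4.

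**When the cap bites.** Take one organ with m measurable lesions, j of them injected.

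- m = 2, j = 1: both lesions are targets, so the un-injected one is measured.
- m ≥ 3, j ≥ 2: both slots can go to injected lesions. Injecting two lesions takes only 2 × 1 mL = 2 mL.
- If the two largest lesions are injected and both can be measured reproducibly, no un-injected lesion in that organ is a target.
- If size rank is unrelated to injection (an assumption; the documents give no frequencies), P(no un-injected target in the organ) = C(j,2)/C(m,2):

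| m | j | Probability |
|---|---|---|
| 3 | 2 | 1/3 = 33% |
| 4 | 2 | 1/6 = 17% |
| 4 | 3 | 3/6 = 50% |
| 5 | 2 | 1/10 = 10% |
| 5 | 4 | 6/10 = 60% |

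For one particular un-injected lesion, such as the one chosen for biopsy, the chance of being non-target is (m − 2)/m: 33% for m = 3 and 50% for m = 4. That holds even when only one lesion is injected. Injected tumours must accommodate the volume (Section 4.1, criterion 7) and dosing follows the longest dimension (Section 6.2), so they will tend to be the larger ones. That is an inference; if right, random rank understates the problem.

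**What is then recorded (assumed sizes).** Injected targets are 40 + 30 = 70 mm and the un-injected non-target lesion is 20 mm.

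- Injected lesions shrink to 28 + 21 = 49 mm: (49 − 70)/70 = −30%, a target PR.
- Un-injected lesion 20 to 10 mm, (10 − 20)/20 = −50%: Non-CR/Non-PD.
- Un-injected lesion unchanged: Non-CR/Non-PD.
- Un-injected lesion 20 to 24 mm, (24 − 20)/20 = +20%: Non-CR/Non-PD, because Appendix B 4.3.1 does not usually count a modest increase as unequivocal progression.

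With no new lesions, the table under Appendix B 4.4 returns an overall PR in all three cases.

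**Two measurable lesions only.** Injected 40 to 20 mm, un-injected 20 mm unchanged: the sum goes from 60 to 40 mm, (40 − 60)/60 = −33%, a PR produced wholly by the injected lesion.

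**Text that might close the gap.** Section 5.12 has all measurable and evaluable lesions re-assessed at each evaluation, but for non-target lesions Appendix B makes that qualitative. Section 5.12.1 permits other skin or palpable lesions to be measured and used as targets without requiring it. Photography covers superficial lesions only. At Weeks 18 to 45 and at Termination the visit lists name injected lesions, whereas the Part 2 schedule (Table 7) names non-injected ones too.

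**The case against.** The best defence is that the trial studies distant activity in other ways. Injected and un-injected lesions are both biopsied at Baseline and Cycle 3, in support of a secondary objective. Non-injected superficial lesions are photographed through the treatment cycles, and Section 5.12.1 asks for a ruler in photographs of skin lesions. Unmodified RECIST v1.1 is a normal choice when the primary endpoint is safety with MTD and RP2D and efficacy is exploratory. The list of exploratory endpoints is not shown in the public text. The Imaging Manual and the detailed SAP to which Section 8.2 defers are not part of the text reviewed. A lesion-level rule may exist there.

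This limits the point without removing it: tissue and photographs are not a required diameter at each tumour assessment. It does rule out several stronger readings that a reader might infer:

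- That every lesion beyond the targets goes unmeasured. Appendix B waives measurement without forbidding it, and follows malignant nodes against 10 mm.
- That the trial cannot distinguish local from abscopal activity. Biopsies and photographs give some evidence, and the relevant endpoints and manuals cannot be seen.
- That nothing keeps the un-injected lesion un-injected. Cycles 2 to 4 ask sites to try to re-inject the previous cycle's lesion, and the Cycle 3 biopsy presupposes an un-injected one. These discourage switching but do not bar it: the same visit lists provide for photographing the former lesion if another is injected.
- That progression is missed in the 20 to 24 mm example. The 4 mm rise is below the 5 mm absolute increase that Appendix B 4.1 requires, so it would not be PD by size even in a sole target. What is lost is the measurement.

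**Conclusion.** The point stands as a gap in a measurement rule. It arises where at least three measurable lesions share an organ and the targets taken there are injected lesions. It does not arise from the cap when there are exactly two measurable lesions, one of them injected, and the requirement that targets represent all involved organs makes it less likely when the un-injected lesion lies in a different organ. A second lesion that is evaluable but below the size for measurability also receives only a qualitative entry. Pooling is the wider limitation: whenever injected and un-injected lesions share one sum, the overall category does not show which of them changed.

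How many subjects are affected cannot be determined, since the documents give no distribution of lesion counts or sites; the percentages above rest on the random-rank assumption. The primary safety and dose-finding objectives are untouched. This is an inexpensive improvement that should be made, conditional on the Imaging Manual or SAP not already containing such a rule.

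**What to change.** In Appendix B 3.1 and Section 5.12:

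- Name at Screening at least one measurable un-injected lesion, where one exists, as an index lesion, and measure it at every tumour assessment whatever its target status.
- Record injected or un-injected status for each lesion at each cycle, counting a lesion as injected from its first injection.
- Report the sums for injected and un-injected lesions separately, beside the overall RECIST v1.1 response, which stays as it is.

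Reconcile the photography wording at Weeks 18 to 45 and at Termination (Section 5.4) with the Table 7 row. If the Imaging Manual or SAP already has a lesion-level rule, bring Appendix B into line with it.

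The cost is one or two extra diameters on scans already scheduled, small eCRF changes and matching wording in the protocol and Imaging Manual. No dose, visit or RECIST category changes.
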